Trauma patients exhibit a wide range of symptom profiles, making it essential to evaluate appropriate measures for assessing treatment outcomes (26). This heterogeneity is evident in the varying patterns of neural activation observed among patients. Incorporating physiological measurements provides objective indices to investigate treatment responses more accurately (27). **The complexity of trauma-related symptoms cannot be fully captured through quantitative data alone and there is a need to assess a more comprehensive understanding of treatment outcomes (26). Employing a mixed methods design that includes participants' own interpretations and understandings of quantitative results adds significant value and is a novel contribution to the research community (28).** Given the centrality of personal meaning in recovery-oriented practice, our application of a phenomenological perspective in researching this treatment represents a significant innovation (29).

2. Hypotheses, aims and objectives

The overall goal of this project is to ensure the quality of the novel TYSB intervention and lay the ground for a larger-scale RCT of the intervention. The project's overall goal is dispersed into three main aims, each in correspondence with a sub-study (study A, B and C):

Aim 1 (Study A): To investigate the lived experiences of participants in the intervention groups to evaluate the acceptability of the TYSB intervention and identify modifications required to improve the intervention.

Research question (RQ1): What are the participants lived experiences and perceptions of the intervention, and how do they react to any positive or negative impacts attributed to it?

Aim 2 (Study B): To explore the experiences and perspectives of partners of the participants in the intervention groups, with the aim of identifying areas for potential improvement in the intervention and specifically how partners can best be involved in the rehabilitation process.

RQ2: What are the partners' experiences of participating in the intervention and of being witness to and taking part in their partners (participants) process during the intervention?

Aim 3 (Study C): To establish foundational data, methodologies, and effect sizes for a subsequent full-scale RCT.

RQ3: What are the changes in patient-reported levels of PTSD symptoms, sexual satisfaction, sexual shame, interoceptive awareness and reactions to touch from pre intervention to post-intervention and at a 3-month follow-up?

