RQ4: How do the capabilities for regulating the autonomic nervous system measured by cardiovascular measurement (ECG) during a script-driven imagery (SDI) procedure change from before to after treatment and at follow-up?

RQ5: What is the adherence rate (recruitment, dropout, and attendance rates among participants) to the intervention?

RQ6: How do the participants interpret and reflect on the quantitative data collected at pre-post intervention and follow-up, with a specific focus on data that stands out or are unexpected in relation to their lived experiences?

Hypothesis (H1): Measurements will show improvements in PTSD symptoms, sexual satisfaction, sexual shame, interoceptive awareness and capability to enjoy touch after the intervention and at follow-up compared to baseline.

H2: Cardiovascular measurement (ECG) during a script-driven imagery (SDI) is a promising method for testing in a RCT.

H3: The study will demonstrate that it is feasible to recruit participants and that at least 80% of them complete the intervention and the study

H4: Participants' reflections will generate new knowledge concerning trauma treatment evaluation identifying relevant primary outcome measures for a larger-scale RCT study.

3. Approach

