Qualitative data analysis (study A, study B and the qualitative part of study C): Qualitative data will be analyzed using Giorgi's descriptive phenomenological method: (1) reading descriptions to grasp the whole, (2) dividing into meaning units, (3) identifying invariant, general meanings in psychological terms, and (4) synthesizing them into a general meaning structure (40). To ensure that the results are reliable, valid and credible, both supervisors will read all the interviews, critically assess the PhD candidate's analysis, and discuss and resolve any discrepancies in interpretation.

Quantitative data analyses (study C):

Quantitative data will be analyzed through linear mixed model analysis (procedure MIXED in SPSS) for statistical comparison of pre-post and follow-up changes in psychometric variables and physiological reactivity. Paired samples t test (two-tailed) will be used for statistical comparison. Due to the small sample size and explorative nature of the study, no statistical correction for multiple testing will be applied. To ensure a 95% confidence interval, analyzes will be performed with a bootstrapping technique. Missing responses will be handled through multiple imputation techniques. Overall significance level set at .05.

Figure 1: The projects study design

The doctoral thesis will utilize collected data and results to draw comprehensive conclusions about the TYSB interventions overall feasibility and associated risks and complications. These conclusions will inform the design of a future RCT, including power calculations, as well as primary outcomes, generating hypotheses, and providing insights into necessary modifications to optimize the TYSB intervention and its protocol, thereby improving validity and reliability.

Potential weaknesses and risks

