We recognize the potential risk of participant drop-out. To ensure enough participants there will be conducted an interim analysis post intervention. A third group will be included in autumn 2026 if there is a larger dropout of women (>3) or less partners (<10) than expected or if the interim analysis reveals that a larger N is needed for designing an adequately powered future study. A potential source of bias in this study stems from the dual role of the PhD candidate, who is also developer of the treatment intervention. This overlap can introduce bias, affecting the impartiality of the study. To mitigate these risks, several strategies have been implemented: Independent therapists conduct the intervention groups, eliminating direct involvement from the researcher. In *studies A* and *B*, interviews are conducted by a co-researcher and user participant unconnected to the intervention, safeguarding impartial data collection and encouraging honest feedback. The analysis of the qualitative data will be done by the PhD candidate in close collaboration with the main supervisor and the co-supervisor who have no connection to the development of the

intervention and no financial interests in the project. It is considered that the PhD candidate's in-depth knowledge of both the intervention and the topic will strengthen the quality of the analysis. The independent supervisors will thoroughly review all interviews, offering new perspectives and critical reflections. They will validate and challenge methodological choices throughout the entire process to ensure that the results are reliable, valid, and credible. Statistical analyzes of the quantitative data will be carried out by the main supervisor in collaboration with an independent statistician at STHF, who has no connection to the intervention. Quantitative data from the questionnaires will be compared with objective physiological measures and participants own understanding of the results. This triangulation of data sources helps to strengthen the dataset and offers a more robust and unbiased objective assessment of the feasibility and acceptability of the intervention. Collectively, these strategies are essential for ensuring the study's reliability and reducing the likelihood that results will be influenced by the researcher's personal interests or expectations.

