3.4 Plan for activities, visibility and dissemination

Activity	From	To
Approval PVO/REK. Planning, recruitment and implementation of study group 1. Pre- and post-test QUAN data collection. Recruitment of participants (group 2).	Jan 2025	Dec 2025
Study group 1: QUAL data collection for study A and study B	Jan 2026	Feb 2025
Study group 2: Pre-test QUAN data collection, post-test QUAN data collection and QUAL data collection for study A and study B.	Feb 2026	May 2026

Study group 1: Follow-up QUAN data collection, analyzing pre-post and follow-up QUAN data and collecting QUAL data for study C.	Apr 2026	Apr 2026
Study group 2: Follow-up QUAN data collection, analyzing pre-post and follow-up QUAN data and collecting QUAL data for study C.	Aug 2026	Aug 2026
Analysis of data study A and complete article study A.	Feb 2026	Feb 2027
Analysis of data study B and complete article study B. Presenting at a conference.	Jul 2026	Sep 2027
Analysis of data study C and complete article study C.	Jan 2027	Feb 2028
Complete mantle. Dissemination of the project at conferences and open lectures.	Oct 2027	Dec 2028

Plan for dissemination of results

We will disseminate the findings from this study through three scientific articles and presentations at scientific conferences. Potential titles of articles:

Study A: *Voices of transformation: A deep dive into the struggles and successes of reclaiming sexuality after sexual trauma.*

Study B: *Healing together: partners' experiences in the journey of sexual trauma recovery through the intervention Take your sexuality back for sexually traumatized women.*

Study C: *A feasibility mixed methods study of the intervention Take your sexuality back for sexually traumatized women: Preliminary evaluations of efficacy and outcome measurements.*

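### Does the open-ended third trigger for adding a treatment group undermine the pre-post estimates?

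*Protocol*

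**What the plan says.** Section 3.1 plans two groups of ten women (N=20). Under Potential weaknesses and risks it adds: "To ensure enough participants there will be conducted an interim analysis post intervention". A third group follows in autumn 2026 if more than 3 women drop out, if fewer than 10 partners take part, or "if the interim analysis reveals that a larger N is needed for designing an adequately powered future study". The third ground has no outcome, parameter, threshold or target precision.

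The data that such an interim could use are the data of Study C. Its aim in Section 2 is "To establish foundational data, methodologies, and effect sizes for a subsequent full-scale RCT". Hypothesis H1 expects "improvements in PTSD symptoms, sexual satisfaction, sexual shame, interoceptive awareness and capability to enjoy touch after the intervention and at follow-up". Under Data analysis, the changes are compared by mixed model and two-tailed paired t test, without correction for multiple testing, and "Overall significance level set at .05". The results then go forward: "These conclusions will inform the design of a future RCT, including power calculations, as well as primary outcomes".

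The activity plan in Section 3.4 has group 1 follow-up data analysed in April 2026 and, for August 2026, "Study group 2: Follow-up QUAN data collection, analyzing pre-post and follow-up QUAN data and collecting QUAL data for study C". The interim itself is undated, and the activity plan does not link these analyses to it.

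**The concern.** The contrast lies within one sentence: two triggers can be checked by counting, while the third depends on what an analysis shows. What a team needs in order to size a trial is usually an effect size and its standard deviation. Those are the pre-post changes that this study also tests at .05 and hands to the later trial. On the activity plan, both groups' results could be known before an autumn extension.

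If the sample were enlarged because early changes looked weak, and kept at 20 when they looked strong, two things would follow. The ordinary t test would reject too often, because the data get a second chance. The pooled mean change would lean upward, because low early values are diluted with new data and high ones are not. An inflated change passed into a power calculation makes the next trial too small. A reader of the final report could not tell whether an extension had followed retention, precision or the changes themselves.

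**Working it through.** **Inputs from the protocol.** N = 20; two-sided paired t test; alpha 0.05; no multiplicity correction; five self-report outcomes in H1.

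**Assumptions, none given by the protocol.** Third group of ten, so 20 becomes 30; all women pooled; normal change scores; equal correlation of 0.2 to 0.6 between outcomes; one extension decision for all outcomes; no clustering by therapy group. The mixed model, bootstrap and multiple imputation were not simulated.

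**1. The plan's own figure.** With N fixed at 20, the simulated type I error of the paired t test is 0.0498 (400,000 runs), which reproduces .05.

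**2. One outcome, test at 20, extend to 30 under a rule, test again at .05.**

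| Extend when | Type I error |
|---|---|
| observed SD is above its median (mean change not used) | 0.054 |
| 0.05 < p < 0.10 | 0.060 |
| 0.05 < p < 0.20 | 0.070 |
| not significant | 0.077 |

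Starting from 17 completers and going to 27, the last rule gives 0.079.

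**3. Five outcomes sharing one decision (200,000 runs per scenario).** One decision cannot suit every outcome at once, so the average error per outcome is mostly lower.

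| Extend when | Average type I error per outcome |
|---|---|
| any outcome is non-significant | 5.0% |
| a majority are non-significant | 5.1 to 5.6% |
| average standardised change < 0.5 | 5.0 to 5.1% |
| average standardised change < 0.3 | 5.2 to 5.5% |
| one named outcome is non-significant | 5.6 to 5.8% (7.7 to 7.8% for that outcome, 5.0 to 5.3% for the others) |
| all five are non-significant | 7.0 to 7.2% |

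Adding RMSSD and SampEn (seven outcomes) gives 6.8 to 7.1% under the all-null rule and 5.0 to 5.7% under the rest.

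**4. Bias of the mean change.** With one outcome, extended whenever it is not significant, a true change of 0.30, 0.50 or 0.80 SD is estimated on average as 0.32, 0.53 or 0.81. That is an upward shift of 0.01 to 0.03 SD. Under the 0.05 < p < 0.20 rule the shift lies between -0.006 and +0.008 SD. With five outcomes and a true change of 0.40 SD, the average shift is +0.003 to +0.022 SD, and +0.027 SD for a single deciding outcome.

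**5. Yardsticks.**
- The 95% half-width of a mean change in SD units is t(.975, n-1)/√n. At n = 20 it is 2.093/4.472 = 0.47; at n = 30 it is 2.045/5.477 = 0.37. The largest shift for a single deciding outcome at 0.40 SD is 0.027/0.47 = 6% of the first half-width.
- Five uncorrected tests, if independent, give at least one false positive with probability 1 - 0.95^5 = 0.226. The protocol accepts that openly.

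**6. Effect on a later power calculation.** Required N varies as 1/d². If a true 0.40 is read as 0.427, N comes out at (0.40/0.427)² = 0.88 of what is needed. Sampling error alone, at n = 30, spans 0.40 ± 0.37, that is 0.03 to 0.77. The upper end alone would cut N to (0.40/0.77)² = 0.27 of what is needed, and the lower end would multiply it more than a hundredfold.

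**The case for a change.** The best argument for a change is that this is not a detail left out for the analysis plan to supply. The protocol itself chose to state the extension rule, put numbers on two of its parts and left the third open. The same section is at pains to limit the influence of the developer's expectations, and an open rule works against that. A clarifying clause would cost one sentence and no participants. An estimate that leans upward also goes straight into the planning of the next trial.

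The asymmetry stands, and so does the point about interpretability. The rest carries less weight. The trigger is tied to the N of a future study and introduced as a means of securing enough participants. That fits questions about retention, the standard deviation and the pre-post correlation at least as well as it fits significance in this study. The quantity used at an interim look is commonly set in an analysis plan. The quantitative analysis lies with the main supervisor "in collaboration with an independent statistician at STHF, who has no connection to the intervention", which does not define the rule but keeps the decision from resting on the developer's analysis alone.

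The stronger remedies would cost something. A rule based on completers would largely repeat the dropout trigger, since more than 3 dropouts already means fewer than 17 of 20. Nor can the interim be dismissed because the relative precision of a standard deviation depends only on n (95% limits of 0.76 to 1.46 times the SD at 20, 0.80 to 1.34 at 30). That holds under normality, which is doubtful for body-map percentages, and only if the SD is the sole planning question. The precision of a correlation depends on its observed value: at n = 20 the Fisher 95% interval is 0.07 to 0.77 for r = 0.5, but 0.55 to 0.92 for r = 0.8. An interim can therefore inform planning without any look at mean change.

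**Conclusion.** The third trigger is loosely worded, but no change to the plan follows. It is a gap that an analyst can fill sensibly: decide on retention or on the precision of planning parameters, and say in the report why a third group was added. Nothing in the protocol directs a decision on observed changes. If one were made that way, type I error per outcome would average 5.0 to 5.8% under most rules and about 7% under the harshest, with 7.7 to 7.9% for a single outcome driving the decision. The upward bias would be at most about 0.03 SD, well inside sampling error at 20 or 30 women. In a single-arm feasibility study that declares itself explorative and applies no multiplicity correction, the results and conclusions would be essentially the same.

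This rests on the assumed third group of ten, normal change scores, ordinary t tests on pooled data and no clustering by therapy group. It would not carry over to a study that made a confirmatory claim from the same tests.

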3.2. Participants, organization and collaborations

The TYSB intervention and the research project are developed and rooted in STHF. The project leader and the PhD-candidate are employed at STHF where the TYSB intervention is carried out. The project builds on collaboration with University in Agder (UiA), Norwegian University of Science and Technology (NTNU), Modum Bad Trauma Clinic in Oslo and three user participants. The PhD candidate will be responsible for day-to day organizing of the project, in close collaboration with the project group. She will have the main responsibility for collecting self-report measurements and physiological measurements, conducting the interviews exploring participants understanding of quantitative data (study C), analysis of qualitative data and dissemination of results. The project group will meet monthly, and the meeting minutes will be documented. The steering committee will meet regularly.

Steering committee

[name], chief for the clinic of mental health and substance abuse treatment, STHF. **[name]**, head of DPS department, STHF. **[name]**, project leader. **[name]** PhD-candidate. **[name]**, user participant.

Project group

3.4 Plan for activities, visibility and dissemination

Activity	From	To
Approval PVO/REK. Planning, recruitment and implementation of study group 1. Pre- and post-test QUAN data collection. Recruitment of participants (group 2).	Jan 2025	Dec 2025
Study group 1: QUAL data collection for study A and study B	Jan 2026	Feb 2025
Study group 2: Pre-test QUAN data collection, post-test QUAN data collection and QUAL data collection for study A and study B.	Feb 2026	May 2026

Study group 1: Follow-up QUAN data collection, analyzing pre-post and follow-up QUAN data and collecting QUAL data for study C.	Apr 2026	Apr 2026
Study group 2: Follow-up QUAN data collection, analyzing pre-post and follow-up QUAN data and collecting QUAL data for study C.	Aug 2026	Aug 2026
Analysis of data study A and complete article study A.	Feb 2026	Feb 2027
Analysis of data study B and complete article study B. Presenting at a conference.	Jul 2026	Sep 2027
Analysis of data study C and complete article study C.	Jan 2027	Feb 2028
Complete mantle. Dissemination of the project at conferences and open lectures.	Oct 2027	Dec 2028

Plan for dissemination of results

We will disseminate the findings from this study through three scientific articles and presentations at scientific conferences. Potential titles of articles:

Study A: *Voices of transformation: A deep dive into the struggles and successes of reclaiming sexuality after sexual trauma.*

Study B: *Healing together: partners' experiences in the journey of sexual trauma recovery through the intervention Take your sexuality back for sexually traumatized women.*

Study C: *A feasibility mixed methods study of the intervention Take your sexuality back for sexually traumatized women: Preliminary evaluations of efficacy and outcome measurements.*

3.4 Potential for implementation

The results will be used to develop a full-scale RCT study and to further develop and use TYSB in clinical practice. We experience a great demand for the treatment and receive referrals from other admission areas outside STHF. To address this demand, we will carry out training for health personnel at other health institutions. This initiative will lay the groundwork for a multi-center study and expand the reach and applicability of the TYSB intervention. Given the critical need for research on treatment methods for traumatized sexuality, the results have the potential to influence future guidelines and recommendations for treatment. In the final phase of the research project, the researcher and user participants will hold open lectures at women's health centers managed by NKS and NOK/SMISO centers. This public engagement is a crucial component of the project, aiming to reduce the taboo surrounding traumatized sexuality, share knowledge and foster a more open and supportive environment for affected individuals and their partners.

4. Budget

Expenses	2025	2026	2027	2028	Total
Wages and social security contributions	732 000	761 000	792 000	823 000	3 108 000
Purchased services/fees	128 000	131 000	115 000	118 000	492 000
Material/equipment	190 000	10 000			250 000
Other expenses	50 000	60 000	90 000	90 000	290 000
Total	1 100 000	962 000	997 000	1 031 000	4 090 000

The researcher will work 25% clinically throughout the project. The PhD project therefore has a timeframe of four years, with 75% of the position being dedicated to research. The study was funded by internal funds in 2025, and funding is being sought for the remaining years, 2026–2028.

5. User involvement

The TYSB intervention has been developed through a collaborative process involving close dialogue with participants from the intervention groups. Five user participants, who have previously participated in the TYSB intervention, were integral to a preliminary project focused on creating a manual for the psychoeducational component of the intervention (25). Their firsthand experiences provided valuable insights that shaped the content of the manual. Two of these user participants continue to contribute to the research study's project group, ensuring continuity and the integration of lived experiences into the project. Additionally, one

user participant, with research experience and no prior connection to the intervention, will participate in the project group bringing a fresh perspective and enhance the objectivity of the research process. The user participants will contribute with interview guides, interviews ([name]), input on data analyses and dissemination of results.

6. Ethical considerations

As standard clinical practice, the patients who are asked to participate in the study have undergone a thorough intake interview which can help them make an informed decision about whether to participate in the intervention and the study. To avoid any pressure, participants are informed about the study by the group therapists, and their decision to participate is communicated to a project secretary. Those who choose not to participate in the study still can receive the same treatment. Participants in the study are informed about their rights to withdraw at any time without needing to explain their reasons. The research interviews, self-rating tools, the SDI procedure, and the intervention itself carry potential risks causing distress. In order to minimize the burden, a critical assessment has been made of which forms and tests are necessary to cover the project's objectives. In accordance with standard clinical practice, the participants will have contact with a therapist outside the group and can thereby receive individual therapy sessions for issues that arise during the interviews, surveys or other assessments. All evaluations and measures will be conducted at the treatment site with the researcher, an experienced trauma therapist, available to manage any trauma reactions. Participants are informed that they can contact the project leader if they need more follow-up. Experiencing ongoing violence is an exclusion criterion for participation in the treatment and the research project. If it is nevertheless discovered, the woman's safety will be prioritized, and the partner will be excluded from the study. Research data will be de-identified, with forms marked by numerical codes. The key linking the codes to participant identities will be stored separately from the research data, in an access-restricted folder at the research server at STHF. All collected data will be stored on Services for Sensitive Data (TSD), University of Oslo. Participants in the study will be allowed to review the transcript of their interviews to ensure the quality of the transcripts and allow them to correct any errors and clarify statements. At the end of the project, de-identified data will be securely stored for five years. The results of the study will be communicated in a way that anonymizes the participants. As a whole, it is considered that this study will lead to greater societal benefit than possible burdens. The project is approved by the Regional Ethics Committee (Reknr 829297) and data protection officer (PVO) and its execution will adhere to the guidelines of the Helsinki and Madrid declarations.
